Appendix 2. Algorithm for Determining ACR Responses

Details presented in this appendix will use “x” as a generic symbol, and the appropriate number (either 20, 50, or 70) is to be filled in when implementing in dataset programming code.

ACRx response is defined as $\geq x\%$ improvement from baseline in tender joint count (68 counts) and $\geq x\%$ improvement in swollen joint count (66 counts), and $\geq x\%$ improvement in at least three of the following five items:

- Patient’s global assessment of arthritis pain;
- Patient’s global assessment of disease activity;
- Physician’s global assessment of disease activity;
- HAQ-DI;
- CRP.

The following abbreviations will be used throughout this appendix to refer to the items needed in the algorithm definitions:

Parameter	Abbreviation for the Parameter
% improvement in tender joint count	TJC68
% improvement in swollen joint count	SJC66
% improvement in patient’s assessment pain	PATPAIN
% improvement in patient’s global assessment of disease activity	PATGA
% improvement in physician’s global assessment of disease activity	PHYGA
% improvement in HAQ-DI	HAQ
% improvement in CRP	CRP

For all seven parameters mentioned above, % improvement at a visit is calculated as:

$(\text{baseline value} - \text{value at visit}) * 100 / \text{baseline value}$.

To calculate the *observed* ACRx response at a visit:

- **Step1:** If the patient discontinued from the study prior to reaching the visit, then STOP – assign ACRx response as blank (ie, missing). Otherwise, calculate the % improvement at the visit for all seven parameters as described above.
- **Step2:**
 - If TJC68 AND SJC66 are BOTH $\geq x\%$, then proceed to step3.
 - If both are nonmissing but one or both is $< x\%$, then STOP – assign the patient as a non-responder for ACRx.
 - If either or both are missing, proceed as follows:
 - a. If both are missing, then STOP – assign ACRx response as blank (ie, missing).
 - b. If one of TJC68 or SJC66 is missing and the nonmissing value is $< x\%$, then STOP – assign the patient as a non-responder for ACRx.

- c. If one of TJC68 or SJC66 is missing and the nonmissing value is $\geq x\%$, then STOP – assign ACRx response as blank (ie, missing).
- **Step3:** Consider the following five variables: PTPAIN, PTDISACT, PHYSDISACT, HAQ, and CRP.
 - If three or more items are missing, then STOP – assign ACRx response as blank (ie, missing).
 - If three or more items are nonmissing, then proceed with the following order:
 - a. If at least three items are $\geq x\%$, then STOP – assign the patient as a responder for ACRx.
 - b. If at least three items are $< x\%$, then STOP – assign the patient as a non-responder for ACRx.
 - c. If less than three items are $\geq x\%$, then STOP – assign ACRx response as blank.

Appendix 3. Algorithm for Calculating Joint Counts

Joints are evaluated and recorded as either non-evaluable, or if evaluable, then if tenderness is present or absent, and if swelling is present or absent. In total, 68 joints are assessed for tenderness and 66 are assessed for swelling. Hips are not assessed for swelling.

The number of tender/swollen joints will be calculated by summing all joints checked to have tenderness/swelling present. If at least half but not all of the joints are evaluable, then the observed prorated joint count will be calculated instead. The prorated scores for TJC will be adjusted based upon the number of evaluable joints: the counted score will be multiplied by 68 then divided by the number of joints evaluated (excluding non-evaluable joints and any joints with a missing response). For example: if only 60 of the 68 joints are assessed to be evaluable at a visit, and 32 of those 60 are tender, the prorated joint count is $(32/60) \times 68 = 36.27$ (not 32). The prorated joint count will be rounded up to the next integer and be used in calculating the percent change from baseline in TJC. The same algorithm will be applied to the calculation of percent change from baseline in SJC with the exception that the counted score will be multiplied by 66 then divided by the number of joints evaluated. If less than half of the joints are evaluable, the number of tender/swollen joints is missing.

This same algorithm will be used for the calculation of TJC and SJC based on 28 joints, which is part of the 28 diarthrodial joint count, based on C-reactive protein (DAS28-CRP) score.

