9.1.2.3.1. American College of Rheumatology Core Set

a. Tender Joint Count

TJC joint assessments will be performed by a blinded assessor.

For ACR measures, the number of tender and painful joints will be determined by examination of 68 joints (34 joints on each side of the patient's body). Any joints that require intra-articular injections during the study (according to Section 7.7) should be excluded from evaluation from the time of the injection to the conclusion of the study.

Joints will be assessed for tenderness by pressure and joint manipulation on physical examination. The patient will be asked for pain sensations on these manipulations and watched for spontaneous pain reactions. Any positive response on pressure, movement, or both will then be translated into a single tender-versus-nontender dichotomy.

Missing, replaced, ankylosed, or arthrodesed joints will be identified by the investigator at the Screening Visit and will be excluded from evaluation during the trial.

b. Swollen Joint Count

SJC joint assessments will be performed by a blinded assessor.

For ACR measures, the number of swollen joints will be determined by examination of 66 joints (33 joints on each side of the patient's body). Any joints that require intra-articular injections during the study (according to Section 7.7) should be excluded from evaluation from the time of the injection to the conclusion of the study.

Joints will be classified as either swollen or not swollen. Swelling is defined as palpable fluctuating synovitis of the joint. Swelling secondary to osteoarthritis will be assessed as not swollen, unless there is unmistakable fluctuation. Dactylitis should be counted as 1 swollen joint.

Missing, replaced, ankylosed, or arthrodesed joints will be identified by the investigator at the Screening Visit and will be excluded from evaluation during the trial.

c. Patient's Assessment of Pain Visual Analog Scale

The patient will be asked to assess his or her current level of joint pain by marking a vertical tick on a 100-mm horizontal VAS where the left end represents no joint pain and the right end represents worst possible joint pain. The Patient's Assessment of Pain VAS should be administered *prior to* the TJC and SJC examinations.

Results will be expressed in millimeters measured between the left end of the scale and the crossing point of the vertical line of the tick; this procedure is applicable for all VAS used in the trial.

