Appendix 1. Abbreviations and Definitions

Term	Definition
ACR	American College of Rheumatology
ACR Core Set	Consists of 7 disease activity measurements: tender joint count, swollen joint count, patient's assessment of pain, Patient's Global Assessment of Disease Activity, Physician's Global Assessment of Disease Activity, Patient's Assessment of Physical Function, and an acute-phase reactant value.
ACR Responder	ACR20 Responder
. Terrasoponav	A patient who has at least 20% improvement in both tender and swollen joint counts and at least 20% improvement in a minimum of 3 of the following 5 criteria: patient's assessment of arthritis pain, Patient's Global Assessment of Disease Activity, Physician's Global Assessment of Disease Activity, Patient's Assessment of Physical Function (Health Assessment Questionnaire-Disability Index), and an acute-phase reactant value (CRP or ESR). ACR50 Responder
	-
	A patient who has at least 50% improvement in both tender and swollen joint counts and at least 50% improvement in a minimum of 3 of the following 5 criteria: patient's assessment of arthritis pain, Patient's Global Assessment of Disease Activity, Physician's Global Assessment of Disease Activity, Patient's Assessment of Physical Function (Health Assessment Questionnaire-Disability Index), and an acute-phase reactant value (CRP or ESR). ACR70 Responder
	=
	A patient who has at least 70% improvement in both tender and swollen joint counts and at least 70% improvement in a minimum of 3 of the following 5 criteria: patient's assessment of arthritis pain, Patient's Global Assessment of Disease Activity, Physician's Global Assessment of Disease Activity, Patient's Assessment of Physical Function (Health Assessment Questionnaire-Disability Index), and an acute-phase reactant value (CRP or ESR).
AE	adverse event: Any untoward medical occurrence in a patient or clinical investigation subject administered a pharmaceutical product that does not necessarily have a causal relationship with this treatment. An adverse event can therefore be any unfavorable and unintended sign (including an abnormal laboratory finding), symptom, or disease temporally associated with the use of a medicinal (investigational) product, whether or not related to the medicinal (investigational) product.
ALP	alkaline phosphatase
ALT	alanine aminotransferase
AST	aspartate aminotransferase

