Nail Psoriasis Severity Index (NAPSI)	NAPSI will be used if the patient has fingernail psoriasis at baseline. The NAPSI is a numeric, reproducible, objective tool for evaluation of fingernail psoriasis. This scale is used to evaluate the severity of fingernail bed psoriasis and fingernail matrix psoriasis by area of involvement in the fingernail unit. In this study, only fingernail involvement will be assessed. The fingernail is divided with imaginary horizontal and longitudinal lines into quadrants. Each fingernail is given a score for fingernail bed psoriasis (0-4) and fingernail matrix psoriasis (0-4), depending on the presence (score of 1) or absence (score of 0) of any of the features of fingernail bed and fingernail matrix psoriasis in each quadrant: 0 = None 1 = present in one quadrant of nail 2 = present in two quadrants of nail 3 = present in three quadrants of nail 4 = present in four quadrants of nail	
 NAPSI score 	The NAPSI score of a fingernail is the sum of scores in fingernail bed and fingernail matrix from each quadrant (maximum of 8). Each fingernail is evaluated, and the sum of all the fingernails is the total NAPSI score (range, 0 to 80), usually indicated as NAPSI score.	For each fingernail, if either the bed or matrix score is missing or not done, then the score for that finger is missing. If <50% of the finger scores from 10 fingers are missing, the imputation will be performed by using the average score of the remaining fingernails. If ≥50% of the finger scores are missing, the NAPSI score will be left as missing
		
 Change from baseline in NAPSI score 	Calculated as: observed NAPSI – baseline NAPSI	Missing if baseline or observed value is missing
		
 NAPSI = 0 	NAPSI score equals to 0, indicating resolution of nail psoriasis.	Single item, missing if observed NAPSI score missing.
Tender Joint Count (TJC) (68 joint count)	The number of tender and painful joints will be determined by examination of 68 joints (34 joints on each side of the patient’s body). The 68 joints to be assessed and classified	
 TJC score 	Adjusted sum of the painful/tender joints for all 68 joints: (sum of the evaluable individual joint	If more than half of the joint scores are nonevaluable, the total score will be missing.

Measure	Description	Variable	Derivation/Comment	Imputation Approach if with Missing Components

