			score of 0 (not tender) or 1 (tender). Otherwise, if the ratio of the circumference of the digit is ≤ 1.1 , then the LDI-B score is set to 0. Tenderness is assessed in the area between the joints. The results of each digit are then added to produce a total score (Healy and Helliwell 2007).	
		
 Change from baseline in LDI-B 	Calculated as: observed LDI-B score – baseline LDI-B score	Missing if baseline or observed value are missing
		
 LDI-B score = 0 	LDI-B score equals to 0, indicating complete resolution in dactylitis.	Missing if observed value is missing
Disease Activity Score based on C-Reactive Protein (DAS28-CRP)	The DAS28-CRP is a measure of disease activity in 28 joints that consists of a composite numerical score utilizing the following variables: TJC, SJC, hs-CRP (measured in mg/L), and PatGA recorded by patients on a 0- to 100-mm VAS. For DAS28-CRP, the 28 joints to be examined and assessed as tender or not tender for TJC (TJC 28) and as swollen or not swollen for SJC (SJC 28) are a subset of those assessed for the TJC and SJC and include 14 joints on each side of the patient’s body: the 2 shoulders, the 2 elbows, the 2 wrists, the 10 metacarpophalangeal joints, the 2 interphalangeal joints of the thumb,	
 DAS28-CRP score 	The following equation will be used to calculate the DAS28 (Vander Cruyssen et al. 2005): $DAS28 - CRP = 0.56(\sqrt{TJC\ 28}) + 0.28(\sqrt{SJC\ 28}) + 0.36(\ln(CRP + 1)) + 0.014(VAS) + 0.96$ Where TJC 28 is calculated as: (sum of the evaluable individual joint scores)/(number of evaluable joints) × 28; SJC 28 is calculated as: (sum of the evaluable individual joint	If one or more variables are missing, then set to missing.

Measure	Description	Variable	Derivation/Comment	Imputation Approach if with Missing Components
	the 8 proximal interphalangeal joints, and the 2 knees (Smolen et al. 1995).		
scores)/(number of evaluable joints) × 28
 
See Appendix 3 for complete details.
	
		
 • DAS28-CRP <2.6 • DAS28-CRP ≥2.6 and <3.2 • DAS28-CRP ≥3.2 and <5.1 • DAS28-CRP ≥5.1 	
DAS28-CRP score falls in intervals
 
<2.6
 
≥2.6 and <3.2
 
≥3.2 and <5.1
 
≥5.1
	Missing if DAS28-CRP score is missing

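### Rounding prorated joint counts up makes a patient whose count exactly halves, with one joint excluded throughout, fail the ACR50 joint criterion

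*SAP*

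**What the plan says.** SAP Appendix 3 applies proration when at least half, but not all, of the joints are evaluable, so a single excluded joint triggers it. The count is scaled to 68 (tender) or 66 (swollen) joints, and then: "The prorated joint count will be rounded up to the next integer and be used in calculating the percent change from baseline in TJC". For swollen joints, "The same algorithm will be applied to the calculation of percent change from baseline in SJC".

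Protocol 9.1.2.3.1 fixes which joints are left out: "Missing, replaced, ankylosed, or arthrodesed joints will be identified by the investigator at the Screening Visit and will be excluded from evaluation during the trial".

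The ACR50 responder in Protocol Appendix 1 is "A patient who has at least 50% improvement in both tender and swollen joint counts", with further conditions on the other core items. SAP 6.12.1.1 and SAP Appendix 2 also use at least 50% for both counts. Under Step 2 of SAP Appendix 2, if either count falls short the instruction is to "assign the patient as a non-responder for ACRx", whatever the other five items show.

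SAP Table RHCF.6.3 describes the tender joint score as "Adjusted sum of the painful/tender joints for all 68 joints" and gives the scaling formula without rounding, but refers to Appendix 3 for complete details. The rounding sentence therefore governs percent change.

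**The concern.** When the same joints are missing at both visits, the scaling factor multiplies baseline and follow-up alike and drops out of the ratio. Proration should then have no effect on percent improvement. Rounding each count up to an integer adds proportionately more to the smaller follow-up count, so a patient who sits exactly on the 50% threshold is pushed below it. The same observed halving passes if every joint is evaluable and fails if the patient has, for example, one replaced joint.

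Both joint counts are mandatory for ACR50. ACR50 is half of the primary endpoint and is the endpoint of the noninferiority test. Entry requires only three tender and three swollen joints, so the low counts, where rounding distorts most, are eligible.

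**Working it through.** **Inputs.** N = 68 (tender) or 66 (swollen); k joints excluded at both visits; proration factor f = N/(N − k); score = count × f rounded up (SAP Appendix 3); improvement = (baseline − visit) × 100 / baseline (SAP Appendix 2); pass if at least 50%; baseline count at least 3 (inclusion criterion 3).

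**The SAP's own example.** 32 tender of 60 evaluable: 32/60 × 68 = 36.27, as printed. The rule turns it into 37.

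**One joint excluded.** A count of c becomes c + c/(N − 1). The added part is above 0 and at most 1, so rounding up always gives c + 1. An exact halving from 2m to m is scored 2m + 1 to m + 1, an improvement of m/(2m + 1), which is always below one half.

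| Observed | Prorated (tender) | Scored | Improvement as scored | Unrounded |
|---|---|---|---|---|
| 4 to 2 | 4.06 to 2.03 | 5 to 3 | 40.0% | 50% |
| 10 to 5 | 10.15 to 5.07 | 11 to 6 | 45.5% | 50% |
| 20 to 10 | 20.30 to 10.15 | 21 to 11 | 47.6% | 50% |
| 66 to 33 | 66.99 to 33.49 | 67 to 34 | 49.3% | 50% |

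Swollen counts of 4, 10 and 20 give the same scored values.

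**More than one excluded.** An exact halving fails when the fractional part of the prorated follow-up count is above 0 and at most 0.5. Exact halvings that fail, out of all possible from a baseline of 3 up:

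| Excluded (k) | Swollen | Tender |
|---|---|---|
| 1 | 31/31 | 32/32 |
| 2 | 15/31 | 15/32 |
| 3 | 19/30 | 20/31 |
| 4 | 14/30 | 15/31 |
| 5 | 17/29 | 17/30 |
| 6 | 14/29 | 14/30 |
| 7 | 16/28 | 16/29 |
| 8 | 13/28 | 13/29 |

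With two excluded, the failures are the even baselines 4 to 32. For baselines 3 to 30 only, 14 of 14 exact halvings fail with one or two excluded, and 6 to 9 of 14 with three to eight excluded.

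**Other pairs of counts.** Enumerating every baseline and follow-up pair, for k up to 33 (swollen) and 34 (tender), no pair other than an exact halving loses response and none gains it. With the same joints out at both visits, the error at the 50% cut runs only toward nonresponse.

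**Joint unscored at one visit only.** Appendix 3 also drops joints with a missing response, so the denominator can differ between visits. Errors then go either way:
- Swollen 3 to 2, one joint unscored at baseline: scored 4 to 2, 50%, a pass. Unrounded: (3.05 − 2)/3.05 = 34%.
- Swollen 3 to 1, one joint unscored at follow-up: scored 3 to 2, 33%, a fail. Unrounded: (3 − 1.02)/3 = 66%.

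**Other thresholds.** The same mechanism reaches ACR20 and ACR70. With one tender joint excluded, 10 to 8 scores 11 to 9 (18.2%) and 10 to 3 scores 11 to 4 (63.6%).

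**DAS28-CRP.** Appendix 3 says "This same algorithm will be used for the calculation of TJC and SJC based on 28 joints", but its rounding sentence is tied to percent change, and Table RHCF.6.3 gives the 28-joint counts unrounded. If rounding were applied, tender and swollen counts of 1 each with one of 28 joints excluded would score (0.56 + 0.28) × (√2 − √(28/27)) = 0.33 too high at that visit.

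**The case against.** The rule is explicit, prespecified and identical in both arms, and the joint counts come from blinded assessors. SAP Version 2 records that the joint-count algorithm was clarified, so rounding up may be deliberate. The protocol is silent on proration. To be misclassified by the same-joints route, a patient needs a non-evaluable joint, a count landing exactly on half, the other joint count passing, at least three of five core items at 50% or better and, for the primary endpoint, PASI 100 as well. The tables above count cells of a grid, not patients. All of that stands, and it is why no effect on a response rate is claimed. It does not reconcile the rule with a definition of at least 50%, and the SAP gives no reason for rounding up.

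Unrounded arithmetic is also not automatically exact. In double precision, with one to eight joints excluded, 7 of 236 swollen and 3 of 244 tender exact halvings still compute to just under 50%. That is a coding tolerance to specify, not a fault in the unrounded rule.

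Protocol 9.1.1.1 as extracted shows a strict greater-than sign for tender joints. Protocol 9.1.2.4, Protocol Appendix 1, SAP 6.12.1.1 and SAP Appendix 2 all use at least 50%, so this is probably a conversion artefact. The swollen-joint result does not depend on it.

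The DAS28-CRP figure is conditional on one reading of the text and is a single-visit error. Baseline would be rounded up too, so the error in change from baseline would be smaller: about 0.17 from counts of 4/4 to 1/1.

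**Conclusion.** The concern holds. As written, Appendix 3 misclassifies patients who meet the ACR50 joint criterion exactly: every exact halving with one joint excluded throughout, and roughly half to two thirds of them with two to eight excluded. This rests on the same joints being out at both visits, as Protocol 9.1.2.3.1 provides, and on a threshold of at least 50%. Any fall larger than an exact halving still passes. The documents do not give the frequency of non-evaluable joints or of exact halvings, so the effect on ACR50 or the primary endpoint cannot be sized; it is probably small. This is a correctable error in a stated derivation, not a threat to the trial's conclusions.

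**What to change.** - **Appendix 3:** replace the rounding sentence with one stating that percent improvement in tender and swollen joint counts is taken from the unrounded prorated count.
- **Programming:** specify a tolerance or an exact integer comparison. With counts b and y on e_b and e_y evaluable joints, the 50% criterion is met when 2 × y × e_b ≤ b × e_y.
- **Sensitivity and reporting:** keep the rounded version as a sensitivity analysis for ACR50 and the primary endpoint, and report by arm the number of patients with any non-evaluable joint.
- **DAS28-CRP:** state that the unrounded 28-joint formulas in Table RHCF.6.3 apply.

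The cost is a short SAP revision, a change to the joint-count step of the ACR derivation and its re-validation. The trial is open-label and this touches the primary responder derivation, so the change should be documented before the Week 24 lock. If Study RHAP used the rounded rule, which the documents do not say, scoring would differ slightly from the source of the planning rates; the sensitivity analysis covers that.

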Appendix 4. Algorithm for Calculating the HAQ-DI

The HAQ-DI is a patient-reported questionnaire to measure disease-associated disability (assessment of physical function). It consists of 24 questions referring to 8 domains: dressing/grooming, arising, eating, walking, hygiene, reach, grip, and activities (Fries et al. 1980, 1982; Ramey et al. 1996).

- **Dressing and grooming** (C1. Dress yourself, including tying shoelaces and doing buttons, C2. Shampooing your Hair)
 - Includes 2 component questions, 1 device checkbox (devices used for dressing), 1 help checkbox
- **Arising** (C1. Stand up from straight chair, C2. Get in and out of bed)
 - Includes 2 component questions, 1 device checkbox (built-up or special chair), 1 help checkbox
- **Eating** (C1. Cut your meat, C2. Lift a cup or glass to your mouth, C3. Open a new carton of milk)
 - Includes 3 component questions, 1 device checkbox (build-up or special utensils), 1 help checkbox
- **Walking** (C1. Walk outdoors on flat ground, C2. Climb up five steps)
 - Includes 2 component questions, 4 device checkboxes (cane, walker, crutches, wheelchair), 1 help checkbox
- **Hygiene** (C1. Wash and dry your body, C2. Take a tub bath, C3. Get on and off the toilet)
 - Includes 3 component questions, 4 device checkboxes (raised toilet seat, bathtub seat, bathtub bar, long-handled appliances in bathroom), 1 help checkbox.
- **Reach** (C1. Reach and get down a 5 pound object (such as a bag of sugar) from just above your head, C2. Bend down to pick up clothing from the floor)
 - Includes 2 component questions, 1 device checkbox (long-handled appliances for reach), 1 help checkbox
- **Grip** (C1. Open car doors, C2. Open jars which have been previously opened, C3. Turn faucets on and off)
 - Includes 3 component questions, 1 device checkbox (jar opener), 1 help checkbox
- **Activities** (C1. Run errands and shop, C2. Get in and out of a car, C3. Do chores such as vacuuming or yard work)
 - Includes 3 component questions, 1 help checkbox

In order to compute the HAQ-DI (Standard Disability Index) score, the following scores are assigned to the responses:

Without any difficulty = 0

With some difficulty = 1

With much difficulty = 2

Unable to do = 3.

The disability section of the questionnaire scores the patient’s self-perception on the degree of difficulty (0 = without any difficulty, 1 = with some difficulty, 2 = with much difficulty, and 3 = unable to do) when dressing and grooming, arising, eating, walking, hygiene, reach, grip, and performing other daily activities. The reported use of special aids or devices and/or the need for assistance of another person to perform these activities is also assessed. The scores for each of the functional domains will be averaged to calculate the functional disability index.

Calculating the HAQ-DI:

The patient must have a score for at least 6 of the 8 categories. If there are less than six categories completed, a HAQ-DI cannot be computed.

- A category score is determined from the highest score of the sub-categories, or components, in that category. (For example, in the category ARISING there are three sub-category items. If a patient responds with a 1, 2, and 0, respectively; the category score is 2.)
- Adjust for use of aids/devices and/or help from another person when indicated :
 - When there are no aids or devices or help indicated for a category, the category’s score is not modified.
 - When aids or devices or help ARE indicated by the patient, adjust the score for a category by increasing a zero or a one to a two. If a patient's highest score for that sub-category is a two it remains a two, and if a three, it remains a three.
 - Sum the eight category scores
 - Divide the sum by the number of categories answered (range 6-8)

The scale is not truly continuous but has 25 possible values (i.e., 0, 0.125, 0.250, 0.375 ... 3).

The mapping of the aids or devices to the categories is the following:

HAQ-DI Category	Companion Aids or Devices Item
Dressing and Grooming	Devices used for dressing (button hook, zipper pull, long handled shoe horn, etc.)
Arising	Built up or special chair
Eating	Built up or special utensils
Walking	Cane, walker, crutches, wheelchair
Hygiene	Raised toilet seat, bathtub seat, bathtub bar, long-handled appliances in bathroom
Reach	Long handled appliances for reach
Grip	Jar opener (for jars previously opened)

